4.2.2 Respiratory Decline Events

During the 28 week study period respiratory decline events are recorded. Such “respiratory decline” events are defined as follows:

- Unscheduled visits to a healthcare professional for respiratory status deterioration.
- Urgent care visit for respiratory status deterioration.
- Hospitalization due to a worsening or exacerbation of respiratory symptoms.

All “respiratory decline” events are characterized according to the definitions of IPF-related acute exacerbation, as proposed by an expert committee sponsored by the IPF Clinical Research Network and the National Heart Lung and Blood Institute (NHLBI) (Collard, Moore et al. 2007) and applied by (Collard, Yow et al. 2013):

- Acute onset of symptoms (< 30 days in duration)
- New radiographic abnormalities (bilateral ground glass or consolidation on HRCT with no pneumothorax or pleural effusion)
- The absence of an identified infectious etiology by routine clinical practice
- Exclusion of alternative causes by routine clinical practice including:
 - a. Left heart failure
 - b. Pulmonary embolism
 - c. Identifiable cause of acute lung injury

Safety will be assessed based on the incidence of “respiratory decline” and further characterized according to the definitions of IPF-related acute exacerbation.

4.2.3 Infusion related reactions

Signs and symptoms of an infusion reaction may include the following: headache, fever, facial flushing, pruritus, myalgia, nausea, chest tightness, dyspnea, vomiting, erythema, abdominal discomfort, diaphoresis, shivers, hypertension, hypotension, lightheadedness, palpitations, urticaria and somnolence. Although unlikely, serious allergic reactions (*e.g.*, anaphylaxis) may occur at any time during the infusion.

Infusion related reactions will be classified by MedDRA Preferred Term (PT) and System Organ Class (SOC). Safety will be assessed based on the incidence of infusion related reactions.

4.2.4 Laboratory endpoints

During the study the following laboratory variables are recorded:

- **Hematology:** Hemoglobin, Hematocrit, Red Blood Cell, White Blood Cell, Neutrophils, Eosinophils, Basophils, Lymphocytes, Monocytes, Platelets.
- **Chemistry:** Sodium, Potassium, Chloride, Glucose, Calcium, AST, ALT, Total Bilirubin, Blood Urea Nitrogen, Bicarbonate, Albumin, Creatinine, Alkaline Phosphatase, Total Protein.
- **Coagulation:** Prothrombin Time, Partial Thromboplastin Time, International Normalized Ratio.

Each laboratory result will be categorized in 3 classes of abnormalities according to (see section 8):

- Normal
- Abnormal NCS
- Abnormal CS

Biological safety will be assessed based on raw test results and change from baseline in raw and categorized laboratory results.

4.2.5 Physical Exams

A complete physical examination is performed during screening and an abbreviated physical exam thereafter. A complete physical examinations will include a review of the following body systems: General appearance, Head, Eyes, Ears, Nose, and Throat, Respiratory, Cardiovascular, Abdomen, Neurologic, Extremities and Dermatologic. Safety will be assessed based on abnormalities (normal, abnormal NCS, abnormal CS) in these body systems.

4.2.6 Vital signs

Vital signs, including Weight, Height, BMI, Heart rate, Respiratory rate, Oxygen saturation, Systolic blood pressure, Diastolic blood pressure are measured in the sitting position at each visit. Vital signs will be assessed based on both raw values and change from baseline to each visit in vital signs measurements. Safety will also be assessed based on abnormalities (normal, abnormal) in vital signs.

4.2.7 Concomitant medication

Concomitant medications will be coded according to the latest available version of the WHO-Drug dictionary and tabulated according to the ATC classification.

5 Statistical and Analytical Methods

5.1 General considerations

The statistical analyses are performed in accordance with the ICH E9 guideline and will be based on the pooled data from the individual study sites, unless otherwise stated. All available efficacy and safety data (according to definition provided in section 4) collected during the randomized phase of the study will be included in data listings and tabulations (i.e., OLE data will not be presented). Except for the analysis of the primary endpoint (see section 5.2.5.1 Primary efficacy analyses) and for selected secondary endpoints (see section 5.2.5.2 for details), all other analyses will be based on observed data only i.e., no missing data will be imputed.

The statistical analyses will be performed by an external Contract Research Organization (CRO), Venn Life Sciences, under the responsibility of the Sponsor.

5.1.1 Presentation of results

The following statistics will be presented:

- For quantitative variables: number of available data, number of missing values, mean, standard deviation, median, Q1, Q3, minimum and maximum values. When relevant, confidence intervals will be calculated for the mean (Student CI) or the median (Hahn & Meeker 1991).
- For qualitative variables: number of available data, number of missing values number and percentage of observations in each category of the variable. Except if otherwise specified, percentages will be calculated using the number of available data as denominator (i.e., not including missing values). When relevant, confidence intervals of proportions will be calculated using the Clopper-Pearson method (Clopper & Pearson 1934).

5.1.2 Significance testing and estimation

For the primary efficacy analysis (see Section 5.2.5.1), the overall type-one error rate will be set to 0.10 two sided. There will be one single primary efficacy analysis, from which the conclusions on efficacy will be drawn. Consequently, there is no issue of multiplicity of primary analyses and no need to adjust the significance level.

For secondary and exploratory endpoint analyses, 90% CIs will be computed. P-values will also be computed for key secondary efficacy endpoints. No adjustment of the type-one error rate will be conducted. As a consequence, the results of these tests will have to be interpreted bearing in mind the issue of multiplicity and the increased risk of erroneously obtaining statistically significant results.

For all fitted models (*i.e.*, Linear Models and Linear Mixed Models), the underlying model assumptions (e.g., homoscedasticity, linearity, independence) and the goodness of fit will be checked graphically.

Missing values will not be imputed for exploratory analyses. Consequently, for all models involving 'Time' effect, the 'Time' variable will be treated as a continuous variable. However, if the analysis of the residuals of a given model suggests departures from the underlying model assumptions, it will be re-fitted considering 'Time' as a categorical variable (8 modalities) in order to explore non-linear trend in response variable.

5.2 Planned analysis

5.2.1 Demographics and baseline characteristics

The following demographics variables will be summarised by treatment group on the ATS, SAF and the PP analysis data sets (Statistical tables 14.1.1 to 14.1.3):

- Gender
- Age
- Ethnicity / Race
- Number of years since diagnosis of IPF

The following baseline characteristics will be summarised by treatment group on the ATS analysis data set:

- Vital signs (including Weight and Height) at baseline by treatment group (Statistical table 14.1.2)
- Physical exam at baseline by treatment group (Statistical table 14.1.3)
- Haematology at baseline by treatment group (Statistical table 14.1.4)
- Haematology abnormalities at baseline by treatment group (Statistical table 14.1.5)
- Chemistry at baseline by treatment group (Statistical table 14.1.6)
- Chemistry abnormalities at baseline by treatment group (Statistical table 14.1.7)
- Coagulation at baseline by treatment group (Statistical table 14.1.8)
- Coagulation abnormalities at baseline by treatment group (Statistical table 14.1.9)
- Background therapy - Use of nintedanib and pirfenidone prior to baseline (Statistical table 14.1.10)

The following baseline characteristics will be summarised by treatment group on the ATS and the PP analysis data sets:

- King's Brief interstitial Lung Disease (Statistical table 14.1.11.1.1 to 14.1.11.1.2) and Leicester Cough Questionnaire (Statistical table 14.1.11.2.1 to 14.1.11.2.2) results at baseline by treatment group.
- High Resolution Computed Tomography measurements at baseline by treatment group (Statistical table 14.1.12.1 to 14.1.12.2)
- Pulmonary Function Tests at baseline by treatment group (Statistical table 14.1.13.1 to 14.1.13.2)
- Six-minute Walk Test distance at baseline by treatment group (Statistical table 14.1.1 to 14.1.2)
- Pentraxin-2 levels at baseline by treatment group (Statistical table 14.1.15.1 to 14.1.15.2)

The following baseline characteristics will be summarised by treatment group on the SAF, the ATS and the PP analysis set:

- Anti-Pentraxin 2 antibodies (ADA) at baseline by treatment group (Statistical table 14.1.16.1 to 14.1.16.3)
- Baseline Genetic Status by treatment group (Statistical table 14.1.17.1 to 14.1.17.3)
- Biomarker levels at baseline by treatment group (Statistical table 14.1.18.1 to 14.1.18.3)

All demographics variables and genetic characteristics of each patient (when available for analysis) will be reported in listing 16.2.4.1 and 16.2.4.2 respectively.

5.2.2 Patient disposition and study discontinuations

Patient disposition will be described using a table (Statistical table 14.1.19) and a flow chart (Figure 14.1). The following variables will be tabulated :

- Number of randomised patients, total and per treatment group
- Number of randomised patient by visit, total and per treatment group
- Number of randomised patients who completed the study treatment as planned (until the 7th cycle on week 24), total and by treatment group
- Number of randomised patients who prematurely discontinued the study treatment (before the 7th cycle on week 24), total and by treatment group
- Number of randomised patients who prematurely discontinued the study treatment before completing the first three cycles and/or who do not have at least one post-cycle 3 evaluation of the primary efficacy criterion (FVC [% predicted])
- Number of randomised patients withdrawn from the study (before week 28) total and by treatment group

The numbers of patient within each dataset (ATS, PP and SAF), globally and by treatment group, will be provided (Statistical table 14.1.20, Listing 16.2.3.1) along with reasons for exclusion from the ATS and PP populations (Statistical table 14.1.21 and 14.1.22 respectively). Reasons for exclusions from the ATS and PP populations will also be provided in Listing 16.2.3.2, according to ICHE3.

A breakdown of the reasons for study discontinuations (Statistical Table 14.1.23 will be tabulated by treatment group. All reasons for study discontinuations will be provided in Listing 16.2.1.

All protocol deviations classified during the blinded review meeting according to definitions provided in section 3.1.1 (Major deviations) and 3.1.2 (Minor deviations) will be tabulated by treatment group for the ATS (Statistical table 14.1.24 and 14.1.25 respectively). All major and minor protocol deviations will also be provided in Listing 16.2.2, according to ICHE3.

5.2.3 Medical history – Previous and concomitant therapy

All medication will be coded according to the latest available version of the WHO-Drug dictionary at the start of the coding activities. For the study of medical histories/therapy for IPF we will distinguish the one ended before baseline from the ones still present at baseline. More specifically, the following variables will be summarised for the ATS and the SAF analysis data sets:

- Past medical history by treatment group (Statistical table 14.1.26.1 to 14.1.26.2)
- Current medical history by treatment group (Statistical table 14.1.27.1 to 14.1.27.2)
- Previous therapy for IPF by treatment group (Statistical table 14.1.28.1 to 14.1.28.2)
- Current therapy for IPF by treatment group, with information on dose of pirfenidone/nintedanib (Statistical table 14.1.29.1 to 14.1.29.2)
- Previous other therapy by treatment group (Statistical table 14.1.30.1 to 14.1.30.2)
- Current other therapy (Statistical table 14.1.31.1 to 14.1.31.2)

Medical history as well as previous and concomitant therapy for each patient will be respectively reported in Listings 16.2.4.3. and 16.2.4.4.

5.2.4 Extent of exposure and compliance

Compliance with study treatment will be computed for each subject of the ATS and the PP populations as the proportion of the prescribed IMP that has been actually administered (see section 8). Treatment compliance will then be analyzed globally and by treatment group, as a numerical variable as well as a categorical variable (see section 8, Statistical table 14.1.32.1 to 14.1.32.2).

To analyse the extent of exposure the following variables will be summarised by treatment group for the SAF population (Statistical table 14.3.1):

- number of infusions received
- cumulative volume of IP actually infused
- duration (number of days) between first IP administration and last IP administration

The extent of exposure will also be assessed based on Pentraxin-2 levels. Descriptive statistics for raw values at each visit and for changes from baseline to each visit in Pentraxin-2 levels will be computed by treatment group. This analysis will be performed on both the ATS and the PP dataset (Statistical table 14.3.2.1 to 14.3.2.3, Figures 14.3.1.1 to 14.3.1.2). Individual measurements of Pentraxin-2 levels will be reported in Listing 16.2.6.7.

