6.8. Rationale for the Dose(s) Selected

In a multiple ascending dose study (PRM151F-12GL), PRM-151 administered IV on Days 1, 3, 5, 8, and 15 to subjects with IPF was well tolerated at doses up to 10 mg/kg. Plasma levels of PRM-151 (C_{max} and AUC) were dose proportional across the range of doses from 1 to 10 mg/kg. PRM-151 had a half-life of 21 to 44 hours. The study did not demonstrate a dose response, but was not intended to do so. Based on these findings, a PRM-151 dose of 10 mg/kg was selected for investigation in the current study.

Preclinical dose ranging studies and in vitro potency assays indicate that the effective dose range in humans may be .2-10 mg/kg. Ten mg/kg was selected for this study because it was safe and resulted in a reduction in bone marrow fibrosis in 11 out of 24 subjects with myelofibrosis treated with PRM-151 10 mg/kg either weekly or every 4 weeks.

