7.10.2. Six-minute Walk Test

Exercise tolerance will be evaluate during the 6MWT according to ATS guidelines (ATS 2002) (Appendix B) as per the schedule of events (Appendix A). If possible, 6MWT

should be the last efficacy assessment completed, by the subject. If it is not possible to complete the 6MWT last, then allow a 30-minute recovery time before continuing with the next efficacy assessment. During the open-labeled extension, subjects will have 6MWT measured every twelve weeks.

7.10.3. **High-resolution Computed Tomography**

High-resolution Computed Tomography (HRCT) will be performed at the Baseline and Weeks 28, and weeks 76 and 128 visits for subjects continuing treatment in the extension.

Spirometry will be performed at selected sites to ensure that full inspiration HRCT is at Total Lung Capacity (TLC).

HRCT is to be performed with the subject in the supine position and at full inspiration. Contiguous CT volumetric acquisition will be obtained according to a specified protocol. HRCT scans will be compared using a standardized reading protocol and software to assess treatment-related changes in lung fibrosis.

7.10.4. **Patient Reported Outcomes**

Kings Brief Interstitial Lung Disease questionnaire (K-BILD) (Patel, Siegert et al.) (Appendix D) is a disease specific questionnaire validated to look at the health status of subjects with a variety of forms of interstitial lung disease (ILD). It consists of 15 items. The K-BILD questionnaire will be performed as per the schedule of events (Appendix A). If possible, the questionnaire should be the first assessment completed by the subjects.

Leicester Cough Questionnaire (Birring, Prudon et al. 2003) (Appendix E) a self-completed health related quality of life measure of chronic cough. The LCQ total score ranges from 3 to 21 and from 1 to 7 for physical, psychological and social domains; a higher score indicates a better health-related quality of life. The LCQ questionnaire will be performed as per the schedule of events (Appendix A). If possible, the questionnaire should be the first assessment completed by the subjects.

7.10.5. **Pentraxin-2 Levels**

Blood samples for determination of pentraxin-2 levels are to be collected pre-dose as per the schedule of events (Appendix A).

7.10.6. **Anti-Pentraxin 2 antibodies / Anti-Drug Antibodies (ADA)**

Blood samples for determination of ADA levels are to be collected pre-dose as per the schedule of events (Appendix A).

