12. APPENDIX A SCHEDULE OF EVENTS

		Week 0 (+/-1day)		W4, W8, W12, W16, W20,W24 (+/- 3d)	W28/ EOS (+/- 3d)	W28 (+/- 3d)		W32 (+/- 3d)	W36 (+/- 3d)	W40 (+/- 3d)	W44 (+/- 3d)	W48 (+/- 3d)	W52 (+/- 3d)	Week 56 (+/-3days)	
		Baseline Dosing Day 1	Dosing Days 3, 5	Dosing Day 1	Dosing Day 1	Dosing Day 1	Dosing Days 3, 5	Dosing Day 1	Baseline Dosing Day 1						
Informed Consent	x														
Demographics	x														
Past Medical History	x														
Inclusion/Exclusion	x	x													
Vital Signs (pre and post dose and every 15 minutes for the duration of the infusion)	x	x	x	x	x	x	x	x	x	x	x	x	x	x	x
Physical Exam[1]	x	x		x	x	x	x	x	x	x	x	x	x	x	x
Height (cm)	x														
Weight (kg)	x	x		x		x	x	x	x	x	x	x	x	x	x
Prior/Concomitant Medications	x	x	x	x	x	x	x	x	x	x	x	x	x	x	x
Special list of excluded medications	x	x	x	x	x	x	x	x	x	x	x	x	x	x	x
AE/SAE Assessment		x	x	x	x	x	x	x	x	x	x	x	x	x	x
ECG & Cytokines (ONLY in the event of an IRR after Baseline)		x	x	x			x	x	x	x	x	x	x	x	x
Efficacy Assessment[2]															
Patient Reported Outcomes; K-BILD & LCQ	x	x		x	x	x		x	x	x	x	x	x		

Pulmonary Function Tests (PFTs)	x	x		x	x	x		x	x	x	x	x	x		
DLCO[3]	x	x			x	x									
FRC & TLC by nitrogen washout method[4]	x	x			x	x									
HRCT (with spirometry at select sites)[5]		x			x	x									
6-minute walk test	x	x		x	x	x		x	x	x	x	x	x		
Pregnancy test Each visit after V4 for all WOCBP	x														
Complete Blood Count	x	x		x	x	x				x			x		
Chemistry, BUN/creatinine	x	x		x	x	x				x			x		
Coagulation	x	x		x	x	x				x			x		
Status of baseline genetic characteristics[6]		x													
Anti-pentraxin 2 antibodies (ADA), Pre-dose		x		x	x	x				x			x		
Pentraxin-2 levels, Pre-dose		x		x	x	x				x			x		
Exploratory laboratory assessments (optional)[7]		x			x	x									
PRM-151 dosing[8]		x	x	x		x	x	x	x	x	x	x	x	x	x

		W60	W64	W68	W72	W76	W80	Week 84		W88	W92	W96	W100	W104	W108	
		(+/- 3d)	(+/-3days)	(+/- 3d)												
		Dosing Day 1	Baseline Dosing Day 1	Dosing Days 3, 5	Dosing Day 1											
Informed Consent	x															
Demographics	x															
Past Medical History	x															
Inclusion/Exclusion	x															
Vital Signs (pre and post dose and every 15 minutes for the duration of the infusion)	x	x	x	x	x	x	x	x	x	x	x	x	x	x	x	x
Physical Exam[1]	x	x	x	x	x	x	x	x	x	x	x	x	x	x	x	x
Height (cm)	x															
Weight (kg)	x	x	x	x	x	x	x	x		x	x	x	x	x	x	x
Prior/Concomitant Medications	x	x	x	x	x	x	x	x	x	x	x	x	x	x	x	x

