2.2.3 Exploratory Objectives (EO)

The exploratory objectives of this study are:

- **EO1:** To evaluate the efficacy and estimate the size of effect of PRM-151 relative to placebo in change from baseline to weeks 4, 8, 12, 16, 20, and 24 in FVC [% predicted] and 6 minute walking distance, pooling subjects on a stable dose of pirfenidone or nintedanib with subjects not on other treatment for IPF and separately in subjects on a stable dose of pirfenidone or nintedanib and in subjects not on other treatments for IPF.
- **EO2:** To assess the impact of PRM-151 on disease related symptoms.
- **EO3:** To assess the impact of PRM-151, disease pathogenesis and disease progression on exploratory serum, cellular and genetic biomarkers
- **EO4:** to explore the relationship between PK and select PD parameters

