- Changes in serum and cellular biomarkers and response according to baseline genetic characteristics: [REDACTED] analysis may be provided at a later stage than the rest of the analyses, some or all the corresponding data may not be available at the time of the database lock.

Pharmacokinetic endpoints: Pentraxin levels will be assayed at baseline, before each study dose infusion and on Week 28.

In addition to the above exploratory endpoints specified in the protocol, it has been decided to perform a retrospective collection of pre-study pulmonary function tests data and, depending on the completeness and usability of the obtained data, to provide descriptive analyses of pre-study evolution of PFT, and, if feasible, to conduct exploratory analyses on the relationship between this pre-study PFT data, and any change during the study and treatment effect.

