The relationship between Anti-Pentraxin 2 antibodies (ADA) presence and level of FVC [% predicted] in time will be studied by modelling the influence of presence/absence (and/or level) of ADA in the repeated measures mixed model used for the primary efficacy analysis (see section 5.2.5.1) and if relevant using non-parametric spline functions. The most parsimonious model will be chosen on the basis of the AIC (Statistical table 14.2.25.1 and 14.2.25.2).

Additional exploratory analysis: Baseline characteristics vs. FVC

If data lend themselves to it, additional exploratory analysis will be done to test for interaction between baseline characteristics (e.g., FVC/DLCO/6MWD) and change in FVC.

Exploratory analysis of PK/PD relationship

Descriptive statistics and correlation will be computed to explore the relationship of Pentraxin-2 levels vs FVC [% predicted]/FVC [ml]/slope of FVC ml at week 24 and 28, and the relationship of

Pentraxin-2 vs other PFTs/PROs/6MWT (Statistical table 14.2.26.1 and 14.2.26.2). If relevant the corresponding scatter plot will be produced.

Exploratory analysis of relationship between Pentraxin-2 levels and ADA

Correlation coefficient between Pentraxin-2 levels and ADA titer at week 28 will be computed (Statistical tables 14.2.27.1 and 14.2.27.2) and a scatterplot prepared (using logarithmic coordinates for titers).

Exploratory analysis of acute exacerbations

Tabulation of each type of acute exacerbations will be produced (Statistical table 14.2.28.1.1 and 14.2.28.1.2). Descriptive statistic and Kaplan-meier curve will be computed by treatment group for time to first reported acute exacerbation (Statistical tables 14.2.28.2.1 and 14.2.28.2.2).

Additional exploratory analysis: FVC [% predicted] separately on pirfenidone and nintedanib

The same model as the one for the primary analysis (see section 5.2.5.1) will be used separately on (i) patient on a stable dose pirfenidone and (ii) patient on a stable dose of nintedanib (Statistical table 14.2.20.1.1 to 14.2.20.2.2).

Additional exploratory analysis: time variation in historic FVC [% predicted; ml] measurements:

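### Post-baseline pentraxin-2 samples are pre-dose troughs many half-lives after the last infusion, so they cannot measure PRM-151 exposure or show exposure-response

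*SAP*

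**What the plan says.** **Sampling.** Protocol 7.10.5 collects pentraxin-2 before dosing and refers to Appendix A for the visits. The Appendix A row "Pentraxin-2 levels, Pre-dose" is marked at Day 1, Weeks 4 to 24 and Week 28. The cell for dosing Days 3 and 5 is blank, and no post-infusion sample is scheduled. SAP 4.1.3 describes it differently, as a pharmacokinetic endpoint: "Pentraxin levels will be assayed at baseline, before each study dose infusion and on Week 28".

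**Kinetics.** Protocol 6.8 reports from the multiple ascending dose study that "PRM-151 had a half-life of 21 to 44 hours". It says that peak concentration and AUC were dose proportional, but gives no values.

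**Use.** SAP 5.2.4 lists number of infusions, cumulative volume and duration as the exposure variables (Table 14.3.1) and adds: "The extent of exposure will also be assessed based on Pentraxin-2 levels". Raw values and changes from baseline are tabulated by arm. Under its PK/PD heading, SAP 5.2.5.3 plans descriptive statistics and correlation "to explore the relationship of Pentraxin-2 levels vs FVC [% predicted]/FVC [ml]/slope of FVC ml at week 24 and 28", and also "Pentraxin-2 vs other PFTs/PROs/6MWT", with no week named for the second group (Table 14.2.26). This serves EO4 in SAP 2.2.3: "to explore the relationship between PK and select PD parameters".

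**The concern.** PRM-151 is recombinant human pentraxin-2, and the native protein circulates in every subject (Protocol 1.2). A concentration reflects drug exposure only if enough infused drug is still present when the sample is drawn. Here the dosing interval is four weeks, the half-life is one to two days, and every scheduled post-baseline sample is drawn at the end of the interval.

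If the drug has gone, the by-subject values hold almost no information on how much PRM-151 a subject received. A null correlation with FVC could be read as no exposure-response. A positive one could be read as a drug effect when it only reflects, for example, healthier subjects having higher native levels. The small residual also depends heavily on when the sample is drawn, with no change in the dose received.

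The stakes are limited. EO4 is not among the protocol's exploratory objectives, and SAP 6.3 lists the PK/PD analysis as not initially planned.

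**Working it through.** The plan states no figure for elapsed half-lives or residual drug, so there is none to reproduce.

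**Inputs**
- Half-life h: 21 to 44 h (Protocol 6.8).
- Dosing: Days 1, 3 and 5, then every 4 weeks (Protocol 4.1).
- Visit window: ±3 days (Appendix A).
- Late dosing: within 2 weeks of the scheduled visit (Protocol 6.2).
- Week 28 visit: 4 weeks ±3 days after the last dose (Protocol 5.4). The late-dose rows below therefore apply only to visits up to Week 24.

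**Formula.** Under first-order decay, the fraction of a single-dose post-infusion level remaining at time t is 2^(−t/h). At Week 4 the contributions of Days 1, 3 and 5 are added.

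- Nominal Weeks 8 to 28: t = 28 × 24 = 672 h. 672/44 = 15.3 half-lives, fraction 2.5e-5. 672/21 = 32, fraction 2.3e-10. Adding earlier four-weekly doses does not change these values.
- Nominal Week 4: Day 5 to Day 29 is 24 × 24 = 576 h. 576/44 = 13.1 and 576/21 = 27.4 half-lives. Summing over 576, 624 and 672 h gives 1.9e-4 (44 h) and 6.9e-9 (21 h).

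The last column of the table is 0.10 divided by the 44 h fraction. It is the post-infusion rise, as a multiple of the endogenous level, at which residual drug would equal 10% of that level.

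| Sample | Time since last infusion | Fraction, h = 44 h | Fraction, h = 21 h | Rise needed (44 h) |
|---|---|---|---|---|
| Weeks 8–28, nominal | 672 h | 2.5e-5 | 2.3e-10 | about 4,000× |
| Week 28, 3 days early | 600 h | 7.9e-5 | 2.5e-9 | about 1,270× |
| Week 4, nominal (three doses) | 576 h | 1.9e-4 | 6.9e-9 | 516× |
| Weeks 8–24, both visits at window edges | 528 h | 2.4e-4 | 2.7e-8 | 410× |
| Week 4, 3 days early (three doses) | 504 h | 6.0e-4 | 7.4e-8 | 166× |
| Previous dose 2 weeks late | 336 h | 0.50% | 1.5e-5 | 20× |
| Previous dose 2 weeks late, next visit 3 days early | 264 h | 1.6% | 1.6e-4 | 6.4× |

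**Sensitivity to timing.** Sampling 3 days (72 h) earlier multiplies the residual by 2^(72/44) = 3.1 or 2^(72/21) = 10.8.

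**Sensitivity to half-life.** For 5% to remain at 672 h, h would have to be 672/log2(20) = about 155 h, which is 155/44 = 3.5 times the top of the stated range.

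**Contrast with Days 3 and 5.** A Day 3 pre-dose sample is 48 h after Day 1 and keeps 21% (21 h) to 47% (44 h). A Day 5 pre-dose sample is 48 h after Day 3 and 96 h after Day 1, and keeps 25% to 69%. Apart from late-dose cases, these would be the only pre-dose samples with substantial drug. SAP 4.1.3, read literally, includes them; Appendix A does not.

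**The case against.** **The analysis is exploratory and makes no exposure-response claim.** SAP 5.2.5.3 plans only descriptive statistics and correlation, with no decision rule, and the term exposure-response is not the SAP's. That is so. But the analysis is headed PK/PD and is tied to an objective about PK, and SAP 5.2.4 calls the levels a measure of extent of exposure. The labels invite the wrong reading.

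**Pre-dose timing is disclosed, and the by-arm tables will show whether troughs differ from placebo.** This stands as a reason to keep those tables. Circulating pentraxin-2 is of interest in IPF (Protocol 1.2), and the tables are already titled neutrally. A comparison of arms still says nothing about differences in drug exposure between treated subjects.

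**Everything rests on one half-life range, not stated to be terminal, and the endogenous level is unknown.** This also stands, and it makes the conclusion conditional. At nominal timing the margin is very wide. In the late-dose cases a 20-fold or 6.4-fold rise would suffice, which the documents cannot exclude. Nor is 2 weeks a hard limit: beyond it the sponsor is to be consulted. A dose 3 weeks late with the next visit on date leaves 168 h, or about 7% at 44 h. In such cases the residual reflects visit timing more than dose received, so it is still a poor exposure measure.

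**SAP 4.1.3 may simply be shorthand for dosing visits.** It may. That part is wording to reconcile and no more.

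**Conclusion.** The concern holds, as a minor point. Under Appendix A, every post-baseline pentraxin-2 sample in the randomised period comes at the end of a dosing interval. At nominal timing at most about 0.02% of a single-dose post-infusion level remains at Week 4, and about 0.003% at Weeks 8 to 28. The values are then essentially endogenous protein. They should not be used to assess extent of exposure, and their correlations with outcome cannot show exposure-response.

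This assumes first-order decay at the protocol's half-life of 21 to 44 h. The documents give no endogenous level, peak concentration or assay limit, so the residual cannot be compared directly with the native level. The descriptive by-arm tables are not at fault, and no primary, secondary or safety conclusion is affected.

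**What to change.** 1. **SAP 5.2.4.** Remove the sentence that makes pentraxin-2 an exposure measure, and describe the values as pre-dose trough, mainly endogenous, pentraxin-2. Keep the by-arm tables and figures over time, and the Week 28 correlation with ADA titre in SAP 5.2.5.3. Extent of exposure then rests on number of infusions, cumulative volume and duration, already planned in Table 14.3.1.
2. **SAP 5.2.5.3 and Table 14.2.26.** Drop the PK/PD label, or present the results only as correlations with trough or endogenous level. Name the pentraxin-2 week used for each outcome, and state that the results are not to be read as exposure-response.
3. **SAP 4.1.3 and Appendix A.** Reconcile them on Days 3 and 5. If pre-dose samples from those days exist, they may support an exploratory analysis within the PRM-151 arm. If not, state that EO4 cannot be addressed with the samples collected.

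The cost is a few sentences and one table title before database lock, plus a check of which samples exist. No new visits, blood draws or protocol amendment are needed. The downside is that EO4 is either set aside or rests on first-cycle samples only.
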